#### Protocol:

A randomized, double-blind, placebo-controlled, operationally seamless phase 2/3 clinical study to evaluate the efficacy and safety of HBM9161 weekly subcutaneous injection in patients with primary immune thrombocytopenia

Phase: Operationally seamless Phase 2/3

Country and study center: China, multicenter

#### Rationale:

The onset of primary immune thrombocytopenia is thought to be caused by increased platelet destruction and decreased platelet production due to anti-platelet antibodies. HBM9161 is a fully human anti-FcRn monoclonal antibody that can effectively remove pathogenic IgG, thereby relieving platelet destruction, and result in rapidly increasing platelet counts in patients. This study has an operationally seamless Phase 2/3 design, with a high dose (680 mg), a low dose (340 mg) of HBM9161, and a placebo group in the Phase 2 part. After the completion of Phase 2 part, an appropriate treatment dose will be selected to be further studied in the Phase 3 part, aiming to provide a new treatment option for the patients with primary ITP as early as possible.

#### Study Objectives:

Phase 2: Dose Selection and Efficacy Ev	valuation
Study Objectives:	Study Endpoints:
Primary Objectives	Primary Endpoints
- To evaluate the early efficacy of weekly subcutaneous HBM9161 340 mg and 680 mg treatment in patients with primary immune thrombocytopenia (ITP) to make a go/no go decision for the phase 3 part and select a dose to be further	
 
Proportion of subjects who achieve a response (R) during the period from Week 1 to Week 7.
 

studied in the phase 3 part, the the phase 3 part decision is go.	
Secondary Objectives	Secondary Endpoints

 
To assess the efficacy of weekly subcutaneous HBM9161 340 mg and 680 mg in patients with primary immune thrombocytopenia (ITP).
 
	
 
Proportion of subjects whose platelet count is ≥ 30 × 10^9/L and at least 2 times of baseline at 4 or more visits out of the 6 visits in the period of Week 19 through Week 24, and who had no bleeding events and no rescue treatment prior to those platelet counts
 

	
 
Proportion of subjects who achieve response (R) within 24 weeks
 

	
 
Proportion of subjects who achieve complete response (CR) within 7 weeks
 

	
 
Proportion of subjects who achieve complete response (CR) within 24 weeks
 

	
 
Proportion of subjects who achieve platelet count ≥ 50 × 10^9/L at least 2 times within 7 weeks
 

	
 
Proportion of subjects who achieve platelet counts ≥ 50 × 10^9/L at least 2 times within 24 weeks
 

	
 
Time to Response: time from imitation of treatment to first response (R) or complete response (CR)
 

	
 
Duration of response: time from response (R) or complete response (CR) to first unmet response (R) or complete response (CR)
 

	Note:
	- Reaction (R) is defined as:
	Platelet counts ≥ 30 × 10  /L and at least 2 times of baseline, confirmed by 2 tests (at least 7 days apart) , and no prior bleeding events and no rescue treatment.
	- Complete response (CR) is defined
	as: platelet counts ≥ 100 × 10  /L should be achieved and confirmed in at least 2 tests (at least 7 days apart) without prior bleeding events and no rescue treatment.

Safety Objective	Safety Endpoints

 
To assess the safety of weekly subcutaneous HBM9161 340 mg and 680 mg in ITP patients
 
	
 
Severity and incidence of adverse events during 24 Weeks
 

Exploratory Objectives	Exploratory Endpoints

 
Other efficacy assessments
 
Biomarker assessments
 
Immunogenicity of HBM9161
 
Exploratory characteristics of the pharmacokinetics (PK) of HBM9161 in patients with primary immune thrombocytopenia based on population pharmacokinetic (PopPK) analysis
 
To assess the relationship between HBM9161 exposure and efficacy and adverse events
 
	
 
WHO bleeding score of subjects from baseline to Week 24
 
Change in platelet count over 24 weeks compared to baseline
 
Proportion of subjects with a decrease in ITP concomitant medication over 24 weeks compared to baseline
 
Proportion of subjects treated with rescue therapy within 24 weeks compared to baseline
 
Change in serum IgG, IgM, IgA, albumin levels from baseline to Week 24
 
Anti-platelet autoantibodies: to assess changes compared to baseline of anti-GPIIb/IIIa, anti-GPIb/IX, and anti-GPIa/IIa antibodies.
 
Anti-drug antibodies: to assess changes in serum anti-HBM9161 antibodies compared to predose.
 
Pharmacokinetics evaluation: all data of HBM9161 plasma concentration obtained in this study will be used for the PopPK analysis, which is to establish a PK model to characterize the PK of subcutaneous injection of HBM9161.
 
Dose-response assessment: to explore the correlation between PK/efficacy and PK/safety.
 

Phase 3: Efficacy and Safety Assessme	nt
Primary Objectives	Primary Endpoints

 
To evaluate the efficacy of weekly subcutaneous HBM9161 (dose to be determined) in patients with primary immune thrombocytopenia (ITP)
 
	
 
Proportion of subjects with ≥ 4 visits with platelet counts ≥ 30 × 10 /L and at least 2 times higher than baseline and no bleeding events and no rescue treatment in 6 visits from Week 19 to Week 24.
 

	,
	Note: The primary endpoint of Phase 3 may be reasonably changed based on the data available in Phase 2 to more accurately reflect the long-term efficacy of the product.
Secondary Objectives	Secondary Endpoints

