#### **Study Population:**

Phase 2 part: 36 patients (12 in Group 1, Group 2 and placebo group respectively) are planned to be randomized. If any subject drops out within 7 weeks after the first dose (including Visit 9), the same number of subjects will be enrolled to replace those who has dropped out (up to 6 subjects). The actual group will be assigned and balanced by randomization system..

Phase 3 part: 230 subjects (115 subjects each in the treatment and placebo groups) are planned to be randomized. The sample size may be increased according to the phase 2 part results, but the final sample size will not exceed 400.

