#### Study Drug:

Phase 2 part: HBM9161

-Dose: Group 1: 340 mg; Group 2: 680 mg

- Method and route(s) of administration: The drug will be administered by subcutaneous injection once a week and 4 times per cycle. The number of treatment cycles will be as clinically indicated, with no more than 3 cycles per subject in the overall trial.

Phase 3 part: HBM9161

- Dose: to be determined (based on data from phase 2 part)

- Method and route(s) of administration: The drug will be administered by subcutaneous injection once a week, 4 times per cycle. The number of treatment cycles will be as clinically indicated, with no more than 3 cycles per subject in the overall trial.

Rescue treatment:

- Rescue treatment will be allowed during this study, including an increase in the dose or frequency of existing ITP concomitant drugs, and the addition of intravenous gamma globulin, anti-D immunoglobulin, high-dose glucocorticoid pulse, recombinant human thrombopoietin (rhTPO) or thrombopoietin receptor agonists, vinblastine, platelet transfusion, and plasmapheresis. The use of rescue treatment is based on the investigator's medical judgement and can be referred to the Expert Consensus on the Diagnosis and Treatment of Primary Immune Thrombocytopenia in Adults (2016 Edition), e.g., lifethreatening thrombocytopenia, major bleeding events (WHO Bleeding Score Grade 3 or 4) or the presence of symptoms or signs suggestive of potential bleeding, and should be confirmed by the sponsor. Patients who achieve a response (R) after receiving rescue treatment should be considered nonresponsive when calculated the response rate.

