#### Statistical Analysis:

The primary endpoint in the phase 2 part is the proportion of subjects who achieve a response (R) between the Week 1 and Week 7. Based on data observed in this study and external information available, the sponsor will make following decisions based on the totality of information at the interim analysis at the end of Week 7 in the phase 2 part:

- whether to proceed to the phase 3 part;
- select a dose to befurther studied in the phase 3 part.

Whether to proceed to the phase 3 part will be based on the Go/No-Go decision framework. If at least one dose shows a high likelihood that the target efficacy can be achieved and the safety of this dose is acceptable, the phase 3 part will start. On the other hand, if the efficacy of both doses is shown to be unlikely to be clinically significant, the trial will be terminated and Phase 3 will not be initiated. If the analysis results do not meet any of the two situations above, the subjects will continue to be observed or sample size will be increased to collect more long-term efficacy data to decide whether to enter Phase 3. The dose selection for the Phase 3 will be based on the comparisons of the efficacy, safety and biomarkers between the two doses.

The primary efficacy endpoint in the Phase 2 is set primarily to verify the mechanism of action of the drug. Since the primary efficacy endpoint in the Phase 2 is for short-term efficacy assessment and the primary efficacy endpoint in the Phase 3 is for long-term efficacy assessment, the decision for Phase 3 will consider not only the observed short-term efficacy as measured by the Phase 2 primary efficacy endpoint, but also the long-term efficacy observed in subjects who have partially completed the trial, the predictions of

the long-term efficacy and the duration of efficacy based on the biomarkers, the efficacy and safety of the competitive products, and the safety data observed from this trial.

The primary endpoint of the Phase 3 is the proportion of subjects with a platelet count  $\ge 30 \times 10^{9}$ /L at  $\ge 4$  of 6 visits from Week 19 to 24 and the platelet count is at least twice baseline level, without bleeding events or rescue treatment. The statistical tests for differences in response rates between groups will be performed based on a normal approximation of the binomial distribution without continuity correction.

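### The Phase 3 primary endpoint has no consistent look-back for rescue or bleeding, so a subject rescued before Week 19 can be scored a success

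*Combined protocol and SAP*

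**What the plan says.** The durable-response measure appears three times in the combined protocol and SAP.

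- **Study Objectives, Phase 3 primary endpoint:** at least 4 visits with a count of 30 × 10^9/L or more and at least twice baseline, with "no bleeding events and no rescue treatment in 6 visits from Week 19 to Week 24".
- **Statistical Analysis, the same endpoint:** at least 4 of the 6 visits, "and the platelet count is at least twice baseline level, without bleeding events or rescue treatment". No period is given for the condition.
- **Study Objectives, Phase 2 secondary endpoint:** the same counts at 4 or more of the same 6 visits, "and who had no bleeding events and no rescue treatment prior to those platelet counts".

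Study Drug (rescue treatment) adds a scoring rule: "Patients who achieve a response (R) after receiving rescue treatment should be considered nonresponsive when calculated the response rate". R is defined in Study Objectives by two tests at least 7 days apart. The Phase 3 primary endpoint is not built on it.

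A note to the Phase 3 endpoint keeps it open: "The primary endpoint of Phase 3 may be reasonably changed based on the data available in Phase 2".

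**The concern.** A confirmatory binary endpoint needs one rule for intercurrent rescue. Here the literal Phase 3 wording looks only at the Week 19-24 window, the analysis section is silent on timing, and the Phase 2 wording looks back over all time before the counts.

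Rescue before Week 19 is foreseeable. Study Drug allows it during the study, and it includes raising existing ITP drugs and adding thrombopoietin receptor agonists, which could still be in use at Weeks 19-24. Under Treatment Duration, further cycles go only to subjects who responded and then relapsed, so a first-cycle non-responder has no further study drug to turn to. If such a subject meets the counts after rescue, the literal wording credits the rescue drug's effect to the randomised arm.

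There is a lesser cross-phase consequence. The decision to start Phase 3 weighs not only short-term response "but also the long-term efficacy observed in subjects who have partially completed the trial", and "The sample size may be increased according to the phase 2 part results". If the phases score the same measure differently, what is learned in Phase 2 describes a slightly different endpoint.

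**Working it through.** **1. Scoring the same subject under each wording**

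| Subject | Phase 3, Study Objectives (literal) | Phase 3, Statistical Analysis | Phase 2 wording, if carried over |
|---|---|---|---|
| A: rescue at Week 10 only; qualifying counts in Weeks 19-24 | Success | Undetermined: depends on the period assumed | Failure |
| B: qualifying counts at Weeks 19-22; rescue at Week 23 | Failure if the condition covers all six visits | Failure on an ordinary reading | Success |
| C: rescue at Week 20; qualifying counts at Weeks 21-24 | Failure if it covers all six visits; success if applied visit by visit | Failure on an ordinary reading | Failure |

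The Study Drug rule, if extended beyond R, fails A and C. It does not reach B, where the counts precede rescue, and it does not mention bleeding. For Phase 3 the live ambiguity is A, plus C on a visit-by-visit reading. B is mainly a difference between the phases.

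**2. The planned sample size**

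The 230 (115 per arm, Study Population) cannot be reproduced: the text available gives no alpha, power, response rates or dropout. Everything below is illustration. It uses the stated test (normal approximation, no continuity correction) with pooled variance and an assumed two-sided alpha of 0.05:

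z = (x1/n − x2/n) / √[2p(1−p)/n], with p = (x1+x2)/(2n) and n = 115.

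One subject is 1/115 = 0.87 percentage points.

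**3. Tipping point for an assumed result, active v placebo**

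- 29 v 12 (25.2% v 10.4%): z = 2.93, p = 0.0034.
- Placebo only, five added: 29 v 17, z = 1.98, p = 0.048.
- Placebo only, six added: 29 v 18, z = 1.80, p = 0.072. Six is 6/103 = 5.8% of placebo non-responders.
- Same 5.8% in both arms: 0.058 × 86 active non-responders ≈ 5, giving 34 v 18, z = 2.52, p = 0.012.
- 40 v 12 (z = 4.41): placebo only, it takes 15 of 103 (14.6%) to reach 40 v 27, p = 0.059. The same 14.6% in both arms adds about 11 on active (0.146 × 75), giving 51 v 27, p = 0.0008.

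**4. Assumed range for rescue**

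Inflation of an arm's rate = (1 − rate) × share of non-responders rescued only before Week 19 × share of those who then meet 4 of 6. The assumed shares are 20-40% and 15-30%, so the product runs from 0.03 to 0.12.

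| Rates if earlier rescue means failure | Rates under the window-only reading | Change in difference (points) | Power |
|---|---|---|---|
| 25% v 10% | 27.25% v 12.7% to 34.0% v 20.8% | −0.45 to −1.8 | 85.4% falls to 79.2-61.3% |
| 35% v 10% | 36.95% v 12.7% to 42.8% v 20.8% | −0.75 to −3.0 | 99.7% falls to 99.2-95% |

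Unequal rescue at 35% v 10%: with 40% rescued on placebo and 20% on active, the difference narrows by 3.45 to 6.9 points. With the shares reversed it widens by 1.2 to 2.4.

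**5. Bleeding**

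The same clause governs bleeding. If 10-40% of window-only successes had bled before Week 19, 25% v 10% would become 22.5% v 9% (× 0.90) down to 15% v 6% (× 0.60). Power would then be 80.7% down to 60.6%.

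**The case against.** The best counter-argument is grammatical. The closing phrase of the Phase 3 wording may be only the denominator for the 4 visits, which is the part the six visits play in the other two sentences. The Phase 3 endpoint then states no period for rescue at all and contradicts nothing. This stands as a possible reading, but it leaves the look-back unstated in both Phase 3 places, and the remedy is the same.

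Second, the Study Drug rule shows intent: response after rescue is non-response, and the primary test is described in the same terms: "The statistical tests for differences in response rates between groups will be performed". That points to failing A and C. It narrows the gap without closing it, because the rule is written for R and says nothing about bleeding.

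Third, the endpoint may still be changed after Phase 2, so there is time to settle it. True, but that does not reconcile the current wordings.

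Two stronger readings are tempting. A reader might infer that the plan holds two contradictory definitions of the Phase 3 primary endpoint. It does not: the prior-to-counts wording belongs to a Phase 2 secondary endpoint and scores no Phase 3 subject. A reader might also infer from the tipping point that the result hangs on the wording. That needs every reclassified subject to be on placebo; equal reclassification leaves both examples significant.

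The cross-phase planning harm is also limited. With 12 subjects per arm one subject is 1/12 = 8.3 points, and at the Week 7 interim only some subjects have long-term data.

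**Conclusion.** The point holds as a gap in the definition of the confirmatory primary endpoint. A Phase 3 subject rescued before Week 19 who then meets 4 of 6 counts can be scored a success on the literal wording, against the plan's own approach in the Phase 2 version and in the rescue rule for R. Bleeding has the same gap.

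The size of the effect is unknown. The documents give no rescue, response or bleeding rates, and every figure beyond 0.87 points per subject rests on assumed ones. The illustrations show sensitivity, not an expected bias: equal rescue shrinks the difference by about 0.5 to 3.0 points, and unequal rescue can move it either way. The change should be made because the endpoint is primary and the correction is cheap, not because a particular loss of power has been shown.

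**What to change.** Put one identical sentence in the Phase 3 primary endpoint under Study Objectives and in Statistical Analysis, using the Phase 2 look-back: success is a count of at least 30 × 10^9/L and at least twice baseline at 4 or more of the 6 Week 19-24 visits, with no rescue treatment and no bleeding event from first dose up to those counts. Extend the Study Drug rule, that response after rescue is non-response, to this endpoint by name.

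Report the Week 19-24-only version as a sensitivity analysis, with the number rescued before Week 19 by arm. Whether rescue after four qualifying counts (subject B) also means failure is the sponsor's choice; fix it in writing before unblinding.

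The cost is one sentence in two places, one extended rule and one table. No new data are needed: rescue within 24 weeks and the WHO bleeding score are already exploratory endpoints. The downside is slightly lower response rates in both arms than under the window-only reading, so the 230 should be checked against the chosen wording.

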	•	Dose-response assessment: To explore the correlation between PK/efficacy and PK/safety.

#### Study Design:

A randomized, double-blind, placebo-controlled; Phase 2/3 operational seamless design

#### **Study Population:**

Phase 2 part: 36 patients (12 in Group 1, Group 2 and placebo group respectively) are planned to be randomized. If any subject drops out within 7 weeks after the first dose (including Visit 9), the same number of subjects will be enrolled to replace those who has dropped out (up to 6 subjects). The actual group will be assigned and balanced by randomization system..

Phase 3 part: 230 subjects (115 subjects each in the treatment and placebo groups) are planned to be randomized. The sample size may be increased according to the phase 2 part results, but the final sample size will not exceed 400.

# Main Inclusion and Exclusion Criteria (for both phase 2 and phase 3 parts):

#### Inclusion Criteria:

- 1. Signed written informed consent.
- 2.  $\geq$  18 years of age at the screening visit, male or female.

3. Female patients will be eligible to participate if meeting the criteria below:

a. Non-childbearing potential (i.e., physiologically incapable of pregnancy, including women who have been menopausal for 2 years)

b. Women of child-bearing potential (WOCBP) must have a negative serum pregnancy test at the first visit, and agreed to correctly use one of the following acceptable and effective methods of contraception (i.e., following the approved product label and physician's instructions) throughout the study from the start of study visit (Screening) until 90 days after the last dose:

- Complete abstinence (when consistent with the patient's preference and previous lifestyle); or
- Levonorgestrel implant should be implanted at least 1 month ahead of study drug administration, but implant time cannot be more than 3 years; or
- Progesterone should be injected at least 1 month ahead of that study drug administration; or
- Oral birth control pills (combination contraceptives or progestins only) administered for at least 1 month prior to study drug administration; or
- Dual birth control: condom or cervical cap (diaphragm or cervical cap) with spermicide (foam/gel/cream/suppository); or
- Intra-uterine devices (published data showing an estimated maximum failure rate is less than 1% per year), implanted by qualified physicians; or
- Estrogen vaginal ring; or
- Transcutaneous contraceptive patch.
- 4. Male patients must use effective contraception methods or their heterosexual partners must use effective birth control during their participation in this clinical trial.
- 5. Diagnosis criteria: meet the American Society of Hematology 2011 diagnosis criteria for persistent or chronic ITP. The average number for platelet count at the screening visit and predose platelet count on the day of first dose (at least 1 day apart) is < 30 × 10 /L, and platelet count is not > 35 × 10 /L for any of two tests. No severe bleeding occurs within 4 weeks prior to the screening visit.
- 6. Patients who have received and failed (poor response, or unmaintained response, or relapse) at least 1 first line of ITP therapy (glucocorticoids and/or intravenous gamma globulin), or who are contraindicated, intolerable, or refuse standard therapy.
- 7. This study allows concomitant drugs for the treatment of ITP, detailed requirements are as follows:
  - Glucocorticoids: prednisone or other equivalents ≤ 20 mg/day are allowed within at least 2 weeks prior to the first dose of the study drug, with dose unchanged or regularly reduced;
  - Danazol: The dose remained unchanged within 3 months prior to the first dose of study drug or has been discontinued for at least 2 weeks prior to the first dose of study drug;
  - Immunosuppressants (azathioprine, cyclosporine A, mycophenolate mofetil only): The dose remains unchanged within 3 months prior to the first dose of the

study drug, or has been discontinued for at least 2 weeks prior to the first dose of the study drug;

- Eltrombopag: The dose remained unchanged within 4 weeks prior to the first dose of the study drug or has been discontinued for at least 2 weeks prior to the first dose of the study drug.
- 8. Willing and be able to receive treatment and complete appropriate assessments as required by the protocol, at the discretion of the investigator.
- 9. Clinical laboratory results at screening must be acceptable to the investigator.

#### Exclusion criteria:

- 1. The patient has severe ITP condition at screening, inappropriate for participation in the study as judged by the investigator (e.g., life-threatening platelets decrease, major bleeding events or symptoms or signs suggestive of potential major bleeding events, and requirement of rescue treatment, including intravenous gamma globulin, anti-D immunoglobulin, high-dose glucocorticoid, or plasmapheresis, etc.).
- 2. Has a history of serious allergic disease or known sensitivity to any components of the study drug.
- 3. Other autoimmune systemic diseases beyond ITP.
- 4. Multi-lineage immune cytopenia, such as Evan's syndrome, autoimmune pancytopenia.
- 5. Secondary ITP caused by leukemia; lymphoma; lymphoproliferative disorders; multiple myeloma; drugs (e.g., quinine, heparin); thyroid disease; cirrhosis; HIV infection; hepatitis C; and antiphospholipid antibody syndrome, etc.
- 6. Has received a vaccine within 4 weeks prior to the first dose of the study drug or is scheduled to receive a vaccine during the study.
- 7. Takes anticoagulants or any agents that have antiplatelet effect or can affect thrombopoiesis within 3 weeks prior to the first dose of the study drug.
- 8. Has received transfusion of blood (including platelet transfusion) within 1 week prior to the first dose of the study drug.
- 9. Has received the intravenous gamma globulin, anti-D immunoglobulin, or plasmapheresis within 2 weeks prior to the first dose of the study drug.
- 10. Has received high-dose dexamethasone or high-dose methylprednisolone within 2 weeks prior to the first dose of the study drug.
- 11. Has received recombinant human thrombopoietin (rhTPO) within 4 weeks prior to the first does of the study drug.
- 12. Has received romiplostim within 4 weeks prior to first dose of the study drug.
- 13. Has received splenic tyrosine kinase inhibitors (Syc inhibitors such as fostamatinib) within 4 weeks prior to the first dose of the study drug.
- 14. Has received rituximab or other non-rituximab anti-CD20 drugs within 6 months prior to the first does of the study drug.
- 15. Has been treated with splenectomy within 4 weeks prior to first dose of the study drug.

- 16. Has received biotherapeutic or investigational drugs not mentioned above within 3 months or 5 half-lives of drugs, whichever is longer, prior to the first dose of the study drug.
- 17. Any thromboembolic or embolic events within 12 months prior to the first does of the study drug.
- 18. Plans to take surgery during the study.
- 19. Active infection at the screening visit, or a serious infection (requiring intravenous antimicrobial therapy or hospitalization) within 8 weeks prior to the first dose of the study drug, or any infection requiring oral antibiotics within 2 weeks prior to the first dose of the study drug, or has symptoms due to fever or viral, bacterial (including upper respiratory tract infection), fungal (non-skin sites), or other infection within 1 week before the first dose of the study drug, previous or current human immunodeficiency virus (HIV) or hepatitis C virus (HCV) infection and current hepatitis B virus (HBV) infection. Patients to be enrolled at the screening visit must have negative results for the tests below: HBV surface antigen, HCV antibody, HIV antibody. Patients with negative HBV surface antigen but positive core antibody should be tested HBV-DNA, and patients with clinical significantly HBV-DNA increase should be excluded.
- 20. Has tuberculosis (TB) infection; with a high risk of TB infection; latent TB infection; or a history of TB infection should be excluded. Other patients are required to receive tuberculin test or interferon-gamma release test to rule out active TB infection.
- 21. Serum total IgG < 700 mg/dL at the screening visit.
- 22. Severe anemia (hemoglobin < 90 g/L), leukopenia (white blood cell count < 3 x 10^9/L), neutropenia (absolute neutrophil count < 1.5 x 10^9/L), or coagulation dysfunction (international normalized ratio[INR] > 1.5 or activated partial thromboplastin time [aPTT] > 1.5 times the upper limit of normal range).
- 23. Hepatic insufficiency with one or more of the following criteria met:
  - a. Alanine aminotransferase (ALT) and/or aspartate aminotransferase (AST) > 2 times the upper limit of normal range at the screening visit;
  - b. Total bilirubin > 1.5 times the upper limit of normal range at the screening visit;
  - c. Severe cirrhosis (Child-Pugh grade C).
- 24. Creatinine clearance ≤ 50 ml/min (calculated by the Cockcroft Gault formula) at the screening visit.
- 25. Uncontrolled hypertension, i.e., blood pressure is still higher than 160/100 mmHg after appropriate treatment.
- 26. Severe cardiovascular (including arrhythmias increasing the risk of embolism at discretion of the investigator, such as atrial fibrillation), liver, kidney, respiratory, or hematological disorders, or other medical or mental illness considered to prevent the patients from participating in the study.
- 27. History of malignant tumor, unless cured with appropriate treatment and no relapse for more than 3 years before the first dose of the study drug. Non-melanoma skin cancer in situ that has been completely resected by surgery (e.g., basal cell carcinoma or squamous cell carcinoma) or cervical cancer in situ can be enrolled.

- 28. Pregnant or lactating patients; or those who are going to become pregnant during the study.
- 29. Patients who are alcohol or drug dependence/abuse at present or during the past 1 year, except for nicotine and coffee.
- 30. The investigator/study center personnel directly related to the study, or an immediate relative of the investigator/study center personnel ("immediate family member" means a spouse, parent, child, or sibling [whether biological or legal adoptive relationship]).

